2.5.4 Supportive analyses for primary estimand

2.5.4.1 Sensitivity analyses for primary estimand

First sensitivity analysis estimand: The target population, the primary variable, the treatment of interest, intercurrent events, and the summary measure of this endpoint are the same as those for the primary estimand. To assess the impact of stratification, the two treatment arms will be compared using the unstratified log-rank test. In the summary tables, this approach is referred to as '*unstratified DFS sensitivity analysis*'.

Second sensitivity analysis estimand: the target population, the primary variable, the treatment of interest, intercurrent events, and the summary measure of this endpoint are the same as those for the primary estimand. The two treatment arms will be compared using the stratified log-rank test with stratification factors derived from the clinical database. In the summary tables, this approach is referred to as '*DFS sensitivity analysis with stratification factors from eCRF*'.

Third sensitivity analysis estimand: the target population, the primary variable, the treatment of interest, intercurrent events, and the summary measure of this endpoint are the same as those for the primary estimand. Subjects with two or more times missing tumor assessments will be censored at the last adequate tumor assessment. Algorithm to identify missing tumor assessments are defined in [Appendix 5.6](#). In the summary tables, this approach is referred to as ‘*DFS sensitivity analysis with censoring for two or more missing assessments*’.

2.5.4.2 Supplementary analyses for primary estimand

First supplementary analysis estimand: the target population, the primary variable, the treatment of interest, and intercurrent events are the same as those for the primary estimand. A Cox regression model, stratified by randomization stratification factors, will be fitted to evaluate the effect of the baseline demographic and disease characteristics, which include age (< 50 years vs. (≥ 50 years and < 65 years) vs. (≥ 65 years and < 75 years) vs. ≥ 75 years), gender (Male vs. Female), race (White vs. Black vs. Asian vs. Others (includes “Native Hawaiian or Other Pacific Islander” and “American Indian or Alaska Native”), ECOG status (0 vs. ≥ 1), and smoking history (never vs. former smoker vs. current smoker). In the summary tables, this approach is referred to as ‘*DFS supplementary analysis adjusted for baseline covariates*’.

Second supplementary analysis estimand: the target population, intercurrent events, and the summary measure of this endpoint are the same as those for the primary estimand. The treatment of interest is the randomized treatment (canakinumab arm or placebo arm without any NSCLC antineoplastic therapy post randomization). The primary variable is defined as the time from the date of randomization to the date of the first documented disease recurrence, date of death due to any cause, or date of new NSCLC antineoplastic therapy, whichever occurs first. Any new NSCLC antineoplastic therapy post randomization prior to recurrence/death will be considered as a DFS event (composite strategy). In the summary tables, this approach is referred to as ‘*ANP leading to DFS event supplementary analysis*’.

Third supplementary analysis estimand: the target population, treatment of interest, and the summary measure of this endpoint are the same as those for the primary estimand. The intercurrent event of initiation of post-treatment anti-neoplastic therapies for NSCLC will be handled by treatment policy, i.e., DFS assessments after initiation of post-treatment anti-neoplastic therapies for NSCLC will be taken into account in assessment of treatment effect. In the summary tables, this approach is referred to as ‘*DFS supplementary analysis regardless of ANP*’.

Fourth supplementary analysis estimand: In light of COVID-19 pandemic and its potential impact on treatment effect, an important scientific question of interest is to estimate the treatment effect based on DFS, had COVID-19 pandemic not occurred. The target population, treatment of interest, and the summary measure of this endpoint are the same as those for the primary estimand. The primary variable is defined as the time from the date of randomization to the date of the first documented recurrence or date of death due to non-COVID-19 pandemic reasons, whichever occurs first. The remaining intercurrent events will be handled as follows:

- **Discontinuation of study treatment due to any non-COVID-19 pandemic reasons:** DFS will take into account all DFS events, irrespective of the study treatment discontinuation reasons (treatment policy)
- **Discontinuation of study treatment due to COVID-19 pandemic reasons:** DFS will be censored at the date of the last adequate tumor assessment prior to discontinuation of treatment

due to COVID-19 pandemic (hypothetical strategy). The discontinuation reason due to COVID-19 will be identified from the defined COVID-19 protocol deviations.

- **Medications used for treating suspected or confirmed COVID-19 cases:** DFS will be censored at the date of the last adequate tumor assessment prior to the administration of COVID-19 medication (hypothetical strategy). Details to identify medications in [Section 2.5.4.2.1](#)
- **Death due to COVID-19:** DFS will be censored at the date of the last adequate tumor assessment prior to death due to COVID-19 (hypothetical strategy)

In the summary tables, this approach is referred to as ‘*COVID-19 DFS supplementary analysis*’.

2.5.4.2.1 Medications treating suspected or confirmed COVID-19

The identification of the drug used to treat COVID-19 depends on whether COVID-19 is confirmed or suspected.

For **confirmed COVID-19**, the drug treating COVID-19 is selected based on:

- Drug indication that contains key word "COVID" or "SARS-COV"
- Drug class (CM ATC level 4) is aminoquinolines, protease inhibitors, glucocorticoids, macrolides, antiviral or antiretroviral; or drug name (CM standard medicine name) contains key word “hydroxychloroquine” or “chloroquine”

For **suspected COVID-19**, the drug treating COVID-19 is selected based on:

- AEs with the preferred term of “SARS-CoV-2 test negative” or “suspected COVID-19”
- Drug class (CM ATC level 4) is aminoquinolines, protease inhibitors, glucocorticoids, macrolides, antiviral or antiretroviral; drug name (CM standard medicine name) contains key word “hydroxychloroquine” or “chloroquine”; drug class (CM ATC level 4) is glucocorticoids and drug indication contains key word "PNEUM" or equals to "DYSPNEA"
- Selecting the first drug with start date within a time window of +/- 7 days of AE start date

2.5.5 Subgroup analyses for the primary estimand

If the primary efficacy analysis is *statistically significant*, the primary endpoint of DFS will be summarized for the subgroups specified in [Section 2.2.1](#):

- Median DFS with its 95% CI from Kaplan-Meier estimation of the DFS distribution
- Hazard ratio with its 95% CI using Cox proportional hazards model stratified by randomization stratification factors

Subgroup analyses are intended to explore the consistency (homogeneity) of treatment effect. A forest plot, including sample size, number of events, and HR with its 95% CI, will be produced for subgroups. *p*-values will not be generated.

2.6 Analysis of the key secondary objective

The key secondary objective is to determine whether canakinumab prolongs OS, compared with placebo.

2.6.1 Key secondary estimand

The key secondary endpoint is OS, defined as the time from the date of randomization to the date of death due to any cause. If a subject is not known to have died, then OS will be censored at the last date the subject was known to be alive (on or before the cut-off date). The OS analysis will be based on the FAS and will include all data up to the cut-off date.

The scientific objective guiding the key secondary estimand is to estimate the treatment effect based on the key secondary endpoint of OS for canakinumab compared to placebo for the randomized subjects with completely resected (R0) NSCLC AJCC/UICC v.8 stages II-III A and IIIB (T> 5 cm N2) disease, irrespective of any treatment discontinuation reasons and any post-treatment antineoplastic therapies administered. The justification for the primary estimand is driven by the rationale to assess treatment effect based on overall survival, irrespective of intercurrent events such as treatment discontinuation, new malignancy, and post treatment anti-neoplastic therapies using treatment policy strategy.

The key secondary endpoint analysis will be described by the following five attributes:

1. The **target population** includes all randomized subjects (FAS).
2. The **primary variable** is OS, defined as the time from the date of randomization to the date of death due to any cause.
3. The treatment of interest is the randomized treatment (canakinumab arm or the matching placebo arm) with or without any new anti-neoplastic therapy administered as needed.
4. The remaining **intercurrent event** describes how events that may occur after randomization are considered when assessing the treatment effect.
 - Discontinuation of study treatment: OS will take into account all deaths and assessments, irrespective of the study treatment discontinuation reasons (treatment policy).
 - New primary malignancy: OS will take into account all deaths and assessments, irrespective of the occurrence of any new malignancy (treatment policy)
 - Any unforeseen intercurrent events due to COVID-19 pandemic will be handled by treatment policy strategy.
5. The **summary measure** is the HR for OS between two treatment arms. It will be estimated using Cox proportional hazard model stratified by randomization stratification factors.

2.6.2 Statistical hypothesis, model, and method of analysis

Assumed proportional hazards model for OS, the following statistical hypotheses will be tested *only* if DFS is statistically significant:

H_{02} (null hypotheses): $\Theta_2 \geq 0$ vs. H_{a2} (alternative hypotheses): $\Theta_2 < 0$

Where Θ_2 is the log hazard ratio of OS in the canakinumab (investigational) vs. placebo (control). The analysis to test these hypotheses will involve a stratified log-rank test at an overall one-sided 2.5% level of significance. The stratification will be based on the following randomization stratification factors: AJCC/UICC v. 8 stage IIA versus IIB versus IIIA versus IIIB T>5cm N2 disease; Histology: squamous versus non-squamous; and Region: Western Europe and North America vs. eastern Asia vs. Rest of the world (RoW).

A group sequential design using a Lan-DeMets (O'Brien-Fleming) α -spending function is employed for OS analyses. OS will be tested hierarchically as follows:

- If DFS is statistically significant at the final DFS analysis, OS will be tested. If OS is not statistically significant at this time, an additional IA and final OS analysis will be planned.
- If DFS is not statistically significant at the final DFS analysis, OS will not be tested.

The OS distribution will be estimated using the Kaplan-Meier method. Kaplan-Meier curves, medians OS and its 95% CI will be presented for each arm. The OS Kaplan-Meier estimate along with its 95% CI will be presented by year as well. The HR and its 95% CI for OS will be calculated using a stratified Cox model. The number of subjects censored for OS and their reasons for censoring will be summarized and listed by treatment.

2.6.3 Handling of missing values/censoring/discontinuations

Subjects not known to have died will be censored for 'Lost to follow-up' if the time between their last contact date and the analysis cut-off date is longer than 14 weeks, i.e., the protocol specified interval between the survival follow-up assessments plus 2 weeks.

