Discontinuation from study treatment	Point/time when the subject permanently stops receiving the study treatment for any reason (prior to the planned completion of study drug administration, if any). Subject agrees to the other protocol required assessments including follow-up. No specific request is made to stop the use of their samples or data.
Dosage	Dose of the study treatment given to the subject in a time unit (e.g. 200 mg every 21 days)
Electronic Data Capture (EDC)	Electronic data capture (EDC) is the electronic acquisition of clinical study data using data collection systems, such as Web-based applications, interactive voice response systems and clinical laboratory interfaces. EDC includes the use of Electronic Case Report Forms (eCRFs) which are used to capture data transcribed from source data/documents used at the point of care.
Enrollment	Point/time of subject entry into the study; at which informed consent must be obtained. The action of enrolling one or more subjects
Investigational drug/ treatment	Drug whose properties are being tested in the study.
Medication number	A unique identifier on the label of medication kits
Other treatment	Treatment that may be needed/allowed during the conduct of the study (i.e. concomitant or rescue therapy)
Subject Number (Subject No. NOVDD) Subject Number (Subject No. NCDS)	A unique identifying number assigned to each subject/subject/healthy volunteer who enrolls in the study
Patient-Reported Outcome (PRO)	A measurement based on a report that comes directly from the patient about the status of a subject's health condition without amendment or interpretation of the patient's report by a clinician or anyone else
Period	The subdivisions of the trial design (e.g. Screening, Treatment, Follow-up) which are described in the Protocol. Periods define the study phases and will be used in clinical trial database setup and eventually in analysis
Perpetrator drug	Is the drug which affects the pharmacokinetics of the other drug
Personal Data	Subject information collected by the Investigator that is coded and transferred to Novartis for the purpose of the clinical trial. This data includes subject identifier information, study information and biological samples.
Randomization	The process of assigning trial subjects to investigational drug or control/comparator drug using an element of chance to determine the
	assignments in order to reduce bias.

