4.3 Definition of end of study

The primary analysis of DFS will occur when approximately 392 DFS events are reached, (refer to Section 10.4). At this time, the primary clinical study report (CSR) will be produced.

After the primary analysis of DFS, the study will remain open provided the DFS demonstrates treatment benefit. Subjects still being followed on the study after the primary analysis time point will continue as per the schedule of assessments.

The study will end once the final OS analysis is performed when approximately 504 deaths are observed or when statistical significance is reached for OS analysis at interim analysis (refer to Section 10.7) and the final analysis of study data is conducted. All available data from all subjects up to this cutoff date will be analyzed.

If the primary analysis of DFS does not demonstrate treatment benefit, the follow-up for OS will end.

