7.1.3 Treatment period

The study treatment phase begins on Cycle 1 Day 1 with the first administration of canakinumab/placebo. Subjects will continue their assigned treatment until they complete 18 cycles or experience any one of the following: disease recurrence as determined by the investigator, unacceptable toxicity that precludes further treatment, treatment discontinuation at the discretion of the Investigator or subject, or start of a new antineoplastic therapy, or death, or lost to follow-up, whichever occurs first. Subjects will be assessed as per visit schedule in Table 7-1. All subjects will be followed for AEs and SAEs for at least 130 days following the EOT visit. Subjects will present to the clinical site every 28 days, for a total of five follow-up visits. If disease recurrence is not observed during the treatment phase, subjects will be followed for recurrence during the post treatment surveillance phase for up to five years (see Section 7.2.1).

Visit windows of ± 1 calendar day will be applicable to scheduled study assessments during Cycle 1. Visit windows of ± 3 days from scheduled study assessments during the treatment phase will apply during and beyond Cycle 2 through EOT and Safety follow up visits. For Survival follow up and Post treatment surveillance, visit windows of ± 7 days will apply in years 2 and 3, and visit windows of ± 21 days will apply for years 4 and 5. Imaging assessments will have a ± 14 day window during years 1-3, and ± 21 days in years 4 and 5. For details of assessments, refer to Table 7-1.

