7.1.6.2 Survival

All subjects who discontinue from the study treatment will be followed up every 12 weeks for survival until the final overall survival (OS) analysis or death, lost to follow-up or withdrawal of consent for survival follow-up (see Table 7-1). Additional survival assessments may be performed outside the 12 weeks follow-up schedules if a survival update is required for an interim assessment to meet safety or regulatory needs. The investigator or his designee will collect this survival information and any new anti-neoplastic therapies for all subjects until the final survival analysis. Follow-up can be done via a phone contact.

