“Note: EOT will be included if EOT is performed within 7 days of permanent discontinuation of study treatment”

Safety follow-up phase

Safety follow-up 1	26 days after treatment discontinuation	[EOT visit date+8; EOT date +39]
Safety follow-up 2	52 days after treatment discontinuation	[EOT visit date+40; EOT date +65]
Safety follow-up 3	78 days after treatment discontinuation	[EOT visit date+66; EOT date +91]
Safety follow-up 4	104 days after treatment discontinuation	[EOT visit date+92; EOT date +117]
Safety follow-up 5	130 days after treatment discontinuation	[EOT visit date+118; EOT date +143]

Post treatment efficacy follow-up phase

Post treatment follow-up (Efficacy follow up)	Every 26 weeks in Year 2 and 3; Every 52 weeks in Year 4 and 5	First time window: [upper bound of the last previous time windows with assessment + 1; TA date + TA interval at next visit/2] Otherwise : [TA date - TA interval at this visit/2; TA date+TA interval at next visit/2]
7 days post disease progression (PRO only)	Within 7 days post disease progression	[disease progression date+1; disease progression date +21]
28 days post disease progression (PRO only)	28 days post disease progression	[disease progression date+22; disease progression date +42]

[a] Study Day 1 = randomization date and PRO assessment on Cycle 1 Day1 will be baseline for PRO if randomization date is not Cycle 1 Day1.

Last contact date

The last contact date will be derived for subjects not known to have died at the analysis cut-off using the last complete date among the following (Table 2-2):

Table 2-1 Last contact date data sources

Source data	Conditions
Date of Randomization	No condition

Source data	Conditions
Last contact date/last date subject was known to be alive from Survival Follow-up page	Subject status is reported to be alive, lost to follow-up or unknown.
Start/End dates from further antineoplastic therapy	Non-missing medication/procedure term.
Start/End dates from drug administration record	Non-missing dose. Doses of 0 are allowed.
Date of disease recurrence	No condition
Laboratory/PK collection dates	Sample collection marked as 'done'.
Vital signs date	At least one non-missing parameter value
Performance Status date	Non-missing performance status
Start/End dates of AE	Non-missing verbatim term

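### The fixed 14-week loss-to-follow-up rule for OS and LCSS is too short for years 4–5, gives sponsor-ended follow-up and consent withdrawal no label of their own, and rests on a last-contact list that omits scan and PRO dates

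*SAP*

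**What the plan says.** SAP 2.6.3 assigns the OS censoring reason *Lost to follow-up* to a subject not known to have died "if the time between their last contact date and the analysis cut-off date is longer than 14 weeks". It explains the figure as "the protocol specified interval between the survival follow-up assessments plus 2 weeks". SAP 2.7.1 repeats the rule for LCSS and lists three LCSS censoring reasons: alive, lost to follow-up, and death from another cause.

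Protocol 7.1.6.2 sets the interval: "All subjects who discontinue from the study treatment will be followed up every 12 weeks for survival". Protocol 7.1.3 sets the windows for survival follow-up: ± "7 days will apply in years 2 and 3, and visit windows of" ±21 "days will apply for years 4 and 5". Protocol 7.1.7 does not allow a subject to be considered lost until the site has completed its due diligence.

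Protocol 4.3 adds: "If the primary analysis of DFS does not demonstrate treatment benefit, the follow-up for OS will end". The SAP for the close-out CSR reports that the primary endpoint was not met. It refers to the primary SAP for methods and still lists the OS and LCSS summaries and listings, with a cut-off of 07Feb2023.

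SAP 2.1.1 derives the last contact date from a list of sources and uses it to censor OS. The list includes recurrence, vital signs, performance status, laboratory and adverse event dates and the survival follow-up page. It does not include the date of a recurrence-free tumor assessment or of a completed PRO questionnaire.

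**The concern.** One fixed threshold is applied to a contact schedule whose window triples, from 7 to 21 days, after year 3. A subject who meets every survival contact in years 4–5 can therefore be reported as lost.

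The rule also has nowhere to put two groups who are not lost in the ordinary sense: subjects who withdrew consent, and subjects whose follow-up the sponsor ended. For DFS the same SAP has a separate consent-withdrawal reason (2.5.3), so one subject can be classed as withdrawn for DFS and lost for OS and LCSS. The label is assigned by date arithmetic alone and does not use the due-diligence condition in protocol 7.1.7.

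SAP 2.6.2 and 2.7.1 have these reasons summarized and listed by arm, and readers will judge completeness of survival follow-up partly from them.

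The omitted sources are a different matter, because they can move a censoring date and not only its label. DFS is censored at the last adequate tumor assessment (SAP 2.5.3), whereas OS is censored at a last contact date that does not use that assessment.

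**Working it through.** **Inputs.** Survival contact interval 12 weeks (protocol 7.1.6.2). Windows ±7 days in years 2–3 and ±21 days in years 4–5 (protocol 7.1, 7.1.3). Threshold 14 weeks (SAP 2.6.3, 2.7.1). Close-out cut-off 07Feb2023.

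**The plan's own figure.** 12 + 2 = 14 weeks. This equals interval + 2 × window for a one-week window: 12 + 2×1 = 14. Interval plus twice the window is also how SAP 5.6 defines the gap that marks one missed tumor assessment.

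**Largest permitted gap between two on-schedule survival contacts**

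| Period | Calculation | Weeks | Longer than 14? |
|---|---|---|---|
| Years 2–3 | 12 + 1 + 1 | 14 | No |
| Year 3 into year 4 | 12 + 1 + 3 | 16 | Yes |
| Years 4–5, earlier contact on time | 12 + 3 | 15 | Yes |
| Years 4–5, earlier contact early and next one late | 12 + 3 + 3 | 18 | Yes |

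**Share mislabelled in years 4–5.** Assume each contact is uniform within ±21 days and the cut-off is random. The gap is 84 + U2 − U1 days.

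- P(gap > 98 days) = (42 − 14)² / (2 × 42²) = 784 / 3528 = 22%.
- Mean excess over 98 days = 28³ / (6 × 42²) = 21952 / 10584 = 2.07 days.
- Share of on-schedule living subjects past 14 weeks at the cut-off = 2.07 / 84 = 2.5%. A simulation gave 2.4%.
- With an 18-week threshold the share is 0%. In years 2–3 it is already 0% at 14 weeks.

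**Rough ceiling on numbers.** 507 of 1382 subjects (37%) had been randomized by 05-Feb-2020, so about that many could have reached year 4 by 07Feb2023, before removing deaths and dropouts. 0.025 × 507 ≈ 13 subjects across both arms, if 12-weekly contact was still running.

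**Close-out.** 07Feb2023 − 98 days = 01Nov2022. Every living subject last contacted before that date is labelled lost. The documents give neither the date survival contact stopped nor the primary analysis cut-off, so this number cannot be computed.

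**Omitted date sources.** In the surveillance years, Table 7-1 of the protocol also records vital signs and ECOG status, which are on the SAP list. A scan can follow that visit, within windows, by at most 14 + 7 = 21 days in years 2–3 (imaging ±14, visit ±7) and 21 + 21 = 42 days in years 4–5. OS falls before DFS only if no later listed contact precedes the cut-off.

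**The case against.** The strongest reply is that this is a reporting label with little reach. Much of that stands. Censoring stays at the last date known alive whatever the label, so Kaplan-Meier curves, the log-rank test and hazard ratios do not change. The 14-week rule is right for years 2–3, and visits on treatment and in safety follow-up are far closer together. Protocol 7.1.6.2 allows extra survival contacts outside the 12-week schedule, which would shorten gaps before a cut-off. The close-out has no formal analysis. Nor are the censoring reasons the only evidence on completeness: SAP 2.7.2 summarizes follow-up duration, and SAP 2.3.1 tabulates reasons for study discontinuation from the disposition page.

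A reader might infer something much larger: that subjects who complete 18 cycles have no 12-weekly contact and are seen only at surveillance visits ("Every 26 weeks in Year 2 and 3; Every 52 weeks in Year 4 and 5"), so that many on-schedule completers would be called lost. The support is a glossary entry that places treatment discontinuation "prior to the planned completion of study drug administration, if any". The documents as a whole point the other way. A second glossary entry defines study treatment discontinuation as a permanent stop for any reason. Protocol 7.1.6.2 goes on to collect survival information on all subjects up to the final survival analysis, and protocol 10.7.2 has all subjects followed for OS. Table 7-1 places the IRT discontinuation entry at the cycle 18/EOT visit. The wording is loose, but the better reading is 12-weekly contact for everyone.

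The objection does not answer three things: the year 4–5 mismatch, the missing censoring reasons, and the missing date sources.

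**Conclusion.** The point holds at modest size. The threshold suits years 2–3 and is up to 4 weeks too short in years 4–5, where about 2.5% of on-schedule living subjects would be mislabelled, assuming uniform timing within windows, a random cut-off and no extra contacts. At close-out the rule also merges sponsor-ended follow-up and consent withdrawal with true loss, to an extent the documents do not let one quantify. The omitted scan and PRO dates can put OS censoring before DFS censoring by a small amount.

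The documents do not support a claim that the OS or LCSS treatment comparison is biased by the labels, nor that large fractions of treatment completers would be called lost. The case for acting is that the censoring-reason tables would be more accurate at almost no cost.

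**What to change.** 1. In SAP 2.6.3 and 2.7.1, keep 14 weeks through year 3 and use 18 weeks (12-week survival interval + 2 × 21 days) in years 4–5. Assign the year by the due date of the next survival contact, so that a gap crossing from year 3 to year 4 is covered. Do not tie the threshold to the 26- or 52-week surveillance interval: 52 + 2×3 = 58 weeks would leave someone who had missed four consecutive 12-weekly contacts unlabelled.
2. Add two censoring reasons for both OS and LCSS, consent withdrawal and follow-up ended by the sponsor, and assign them before the loss-to-follow-up rule is applied.
3. Add tumor-assessment and PRO completion dates to the last-contact sources in SAP 2.1.1.
4. Carry the same rules into the close-out outputs.

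The cost is SAP wording and a small derivation change on data already collected. Items 1 and 2 change only reported censoring reasons. Item 3 slightly lengthens observed OS and LCSS follow-up.
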